7.8 Treatment After the End of the Study

At the end of the treatment period as defined in [Section 7.1](#), BMS will not continue to provide BMS-supplied study treatment to participants/investigators unless BMS chooses to extend the study. The investigator should ensure that the participant receives appropriate SOC to treat the condition under study.

8 DISCONTINUATION CRITERIA

8.1 Discontinuation From Study Treatment

Participants MUST discontinue investigational product (and non-investigational product at the discretion of the investigator) for any of the following reasons:

- Participant's request to stop study treatment. Participants who request to discontinue study treatment will remain in the study and must continue to be followed for protocol specified follow-up procedures. The only exception to this is when a participant specifically withdraws consent for any further contact with him/her or persons previously authorized by participant to provide this information
- Any clinical adverse event (AE), laboratory abnormality or intercurrent illness which, in the opinion of the investigator, indicates that continued participation in the study is not in the best interest of the participant
- Termination of the study by BMS
- Loss of ability to freely provide consent through imprisonment or involuntarily incarceration for treatment of either a psychiatric or physical (eg, infectious disease) illness. (Note: Under

specific circumstances and only in countries where local regulations permit, a participant who has been imprisoned may be permitted to continue as a participant. Strict conditions apply and BMS approval is required.)

- Additional protocol-specified reasons for discontinuation (Sections 8.1.1 and [8.1.2](#))
- Disease progression or recurrence locally diagnosed.

Refer to the Schedule of Activities, [Section 2](#), for data to be collected at the time of treatment discontinuation and follow-up and for any further evaluations that can be completed.

In the case of pregnancy, the investigator must immediately, within 24 hours of awareness of the pregnancy, notify the BMS Medical Monitor/designee of this event. In most cases, the study treatment will be permanently discontinued in an appropriate manner (eg, dose tapering if necessary for participant safety). Refer to [Section 9.2.5](#).

All participants who discontinue study treatment should comply with protocol specified follow-up procedures as outlined in [Section 2](#). The only exception to this requirement is when a participant withdraws consent for all study procedures including post-treatment study follow-up or loses the ability to consent freely (ie, is imprisoned or involuntarily incarcerated for the treatment of either a psychiatric or physical illness).

If study treatment is discontinued prior to the participant's completion of the study, the reason for the discontinuation must be documented in the participant's medical records and entered on the appropriate CRF page.

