5.1.3 Follow-up Phase

The follow-up phase will begin when the decision to discontinue a participant from the last study treatment is made (no further study treatment) or when 3 years of study treatment has been completed (eg, a participant may be discontinued from nivolumab/nivolumab-placebo study treatment on or before 24 months but remains on maintenance BCG study treatment for 36 months [see [Sections 5.4.4](#) and [5.4.5](#)]).

Participants must be followed for at least 100 days after last dose of last study treatment.

- Follow-up (FU) visit 1 should occur 30 days from the last dose (± 7) days or can be performed on the date of discontinuation if that date is greater than 42 days from the last dose.
- FU visit 2 occurs approximately 100 days (± 7 days) from last dose of study treatment.
- Both visits should be conducted in person.

Not applicable per Protocol Amendment 01:

Survival follow-up begins after FU visit 2.

- Survival follow-up visits occur every 3 months (± 14 days) until the end of the study.

Not applicable per Protocol Amendment 01:

Efficacy follow-up:

- Efficacy assessments occur until disease recurrence (other than low-grade Ta) or progression, per PRC (based on a positive urinary cytology, bladder biopsy, or imaging), or treatment discontinuation, whichever is later.
- For participants who have not had PRC confirmed progression or recurrence during the on-treatment period, efficacy assessments will continue as per [Table 2-3](#) and [Section 9.1.8](#).
- Where scheduling allows, efficacy follow up and survival follow up can coincide.

Treatment beyond disease recurrence/progression is not permitted except in the case of a low-grade papillary Ta tumor (TaLG) UC recurrence only, or for participants with CIS and/or Ta at Week 13 (see [Section 8.1.4](#)).

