7.1.1 Nivolumab Dosing

Participants should receive nivolumab at a dose of 480 mg as an approximately 30-minute infusion on Day 1 of each treatment cycle until recurrence or progression, unacceptable toxicity, withdrawal of consent, completion of 24 months of treatment, or the study ends, whichever occurs first. If needed, flush the intravenous line with an appropriate amount of diluent (eg, 0.9% Sodium Chloride or 5% Dextrose in water) to ensure that the complete dose is administered over approximately 30 minutes. For participants with CIS and/or TaHG at Week 13 assessment, see [Section 8.1.4](#).

Participants should begin study treatment within 3 calendar days of randomization but no earlier than \geq 14 days following last TURBT/bladder biopsy. Nivolumab/nivolumab-placebo and BCG should begin concurrently or within 3 days of each other. Cycle 1 will begin at the time of the first dose of study treatment.

There should be a minimum of 26 days between nivolumab/nivolumab-placebo doses. There will be no dose escalations or reductions of nivolumab/nivolumab-placebo allowed. For Q4W dosing cycles, participants may be dosed within a \pm 3 day window. Premedications are not recommended for the first dose of nivolumab/nivolumab-placebo.

Participants should be carefully monitored for infusion reactions during nivolumab administration. If an acute infusion reaction is noted, participants should be managed according to [Section 7.7.4](#).

Doses of nivolumab/ nivolumab-placebo may be interrupted, delayed, or discontinued depending on how well the participant tolerates the treatment. Dosing visits are not skipped, only delayed.

Please refer to the current Investigator Brochure and/or Pharmacy Manual for further details regarding storage, preparation, and administration of nivolumab.

Care must be taken to assure sterility of the prepared solution as the product does not contain any antimicrobial preservative or bacteriostatic agent.

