8.1.4 CIS and/or TaHG at Week 13: Continued Treatment

Participants should continue treatment with nivolumab/nivolumab-placebo and BCG until disease recurrence, progression, unacceptable toxicity, treatment discontinuation, or until the end of the defined treatment periods.

In participants with CIS (with or without papillary disease) at baseline, the presence of CIS and/or a positive cytology at the first disease assessment (Week 13) is defined as an EFS event and is

considered equivalent to recurrence. The presence of TaHG is considered recurrence and also defined as an EFS event (see [Section 9.1.1](#)).

Evidence from the BCG-naïve setting suggests⁴⁷ that with continued BCG exposure, many participants with CIS at the first disease assessment respond to continued BCG treatment after the first disease assessment (Week 13) and by the second disease assessment (Week 26). For this reason, study participants who have CIS at Week 13 (either positive cytology, cystoscopy and biopsy findings, or both) may continue treatment until Week 26. Similarly, participants with TaHG at Week 13 may also derive delayed benefit from continued treatment, and may also continue on study treatment until Week 26. TaHG at Week 13 should be treated with TURBT as appropriate in line with SOC.

Participants with CIS and/or TaHG at Week 13 must have no other evidence of recurrence or progression to continue treatment. It is at the investigator's discretion to continue treating such participants based on their clinical assessment of the best interests of the participant and appropriate patient counselling and documented consent, including consideration of alternative treatment options such as cystectomy.

In participants who have CIS and/or TaHG disease at Week 13 and who are treated beyond Week 13, subsequent CIS or recurrent TaHG a will require permanent discontinuation.

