9.1 Efficacy Assessments

Per Protocol Amendment 01, efficacy assessments will be conducted per the local standards of care.

Not applicable per Protocol Amendment 01:

Efficacy assessments occur until disease recurrence (other than TaLG) or progression, per PRC (based on a positive urinary cytology, bladder biopsy, or imaging), or until treatment discontinuation, whichever occurs later ([Table 2-2](#) and [Table 2-3](#)).

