For details on positive/suspicious cytology with a normal biopsy and the assessment of CR, see [Sections 9.1.4.1](#) and [9.1.4.2](#).

The primary endpoint of EFS and the secondary endpoint of CR rate will be based on the Week 13 CR assessment only. DoR will include the Week 13 assessment and subsequent assessments. Exploratory endpoints will examine CR at additional time points (see [Section 4](#)).

9.1.2.4 *Disease Recurrence/Progression*

Per Protocol Amendment 01, disease recurrence and progression will be determined in all participants throughout the duration of the study by the investigator according to local standards of care.

Not applicable per Protocol Amendment 01:

This determination of recurrence or progression will be based on evaluation of urinary cytology and tissue obtained at bladder biopsy, whether the biopsy is performed for cause or as required by

the protocol. Any abnormality in any participant (CIS or non-CIS) discovered on cystoscopic examination of the bladder that is suspicious for recurrent papillary tumor or CIS must be biopsied and evaluated. This biopsy is in addition to the required biopsies in screening and at Week 26 in CIS participants. Protocol-defined or off-schedule imaging may also inform a diagnosis of progression.

Recurrence is defined as the presence of high-risk bladder lesions, including TaHG or T1 UC or CIS in the bladder biopsy specimen. Participants with only TaLG UC on bladder biopsy will not be classified as having a recurrence, per PRC.

Recurrence is also defined as a positive (malignant) urinary cytology, per PRC. A positive urinary cytology should be investigated as detailed in [Section 9.1.4.1](#).

A suspicious urine cytology must be evaluated as described in Sections 9.1.4.1 and [9.1.4.2](#). A suspicious cytology alone does not define recurrence. Participants with an initial suspicious cytology who are found to have a positive (malignant) cytology on repeat testing, high-risk disease on for-cause or random biopsies from the bladder or prostatic urethra (CIS, TaHG, \geq T1), or an upper tract lesion on imaging will be classified as having recurrence/progression on the date of the original suspicious cytology result.

CIS participants with CIS only +/- positive cytology at Week 13 will be classified as having persistent disease. This is considered equivalent to recurrence.

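### Does the mandatory stop at locally diagnosed recurrence in Section 8.1 cancel the Week 13 continuation and leave low-grade Ta findings without a rule?

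*Combined protocol and SAP*

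**What the plan says.** The heading sentence of Section 8.1 makes stopping mandatory for investigational product, which Table 7-1 defines to include both nivolumab and BCG. One reason listed is "Disease progression or recurrence locally diagnosed". The list's only pointer to its own subsections begins "Additional protocol-specified reasons for discontinuation (Sections 8.1.1 and" and ends with 8.1.2, so 8.1.4 is not named there.

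Section 8.1.4 treats CIS at Week 13 as equivalent to recurrence and TaHG at Week 13 as recurrence. It still allows treatment to go on at the investigator's discretion. For CIS it permits continuation to Week 26, and for TaHG it says that "participants with TaHG at Week 13 may also derive delayed benefit from continued treatment, and may also continue on study treatment until Week 26". The condition is that "Participants with CIS and/or TaHG at Week 13 must have no other evidence of recurrence or progression to continue treatment".

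Sections 7.1.1 and 7.1.2 each state that treatment runs until recurrence or progression, among other end points. Each then adds "For participants with CIS and/or TaHG at Week 13 assessment, see" Section 8.1.4.

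On TaLG, the last sentence of Section 5.1.3 begins "Treatment beyond disease recurrence/progression is not permitted except in the case of a low-grade papillary Ta tumor (TaLG) UC recurrence only" and goes on to exempt Week 13 CIS and/or Ta, citing 8.1.4. It comes after efficacy follow-up bullets marked not applicable under Amendment 01. Two other TaLG statements stand under the same kind of label. Section 9.1 says "Efficacy assessments occur until disease recurrence (other than TaLG) or progression, per PRC", and Section 9.1.2.4 says "Participants with only TaLG UC on bladder biopsy will not be classified as having a recurrence, per PRC". The live opening of 9.1.2.4 leaves recurrence to the investigator under local standards of care and does not mention grade.

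**The concern.** There are two apparent conflicts.

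The first concerns Week 13. By 8.1.4's own labels, CIS or TaHG at that visit is recurrence or its equivalent. The same finding then triggers a compulsory stop under 8.1 and a permitted continuation under 8.1.4. The amendment sharpens this, because its change summary shows that the 8.1 bullet was reworded, and Section 3.1.1 says amendment changes override existing requirements where the two appear to clash. A literal reader could take the newer bullet as displacing 8.1.4.

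The second concerns TaLG. If the label in 5.1.3 runs to the end of that section, the only treatment rule naming TaLG is gone. Every other TaLG statement is also marked not applicable, so a site would have only local practice to go on. If the sentence is live, it allows something that 8.1 does not mention. The vocabulary also varies: 5.1.3 and 9.1 treat TaLG as a recurrence that is exempted, while 9.1.2.4 says it is not a recurrence.

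At stake would be whether an individual still on treatment stops or continues, and with that the recorded treatment duration and reason for discontinuation.

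**Working it through.** The plan states no figure on this point, so the check is mainly of text, with arithmetic only to bound the size.

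**Week 13, passages side by side.**

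| Place | Marked not applicable? | Content |
|---|---|---|
| 8.1 bullet | No | Stop at locally diagnosed recurrence or progression |
| 8.1.4 | No | Restates the general rule, then permits continuation from Week 13 to Week 26 |
| 7.1.1, 7.1.2 | No | State the general rule, then refer to 8.1.4 |
| 5.1.3, last sentence | Unclear | Bars treatment beyond recurrence except for TaLG only, or Week 13 CIS and/or Ta; refers to 8.1.4 |

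1. Section 8.1.4 sits inside 8.1, and its title announces continued treatment. A specific subsection qualifies the general list of its parent section.
2. The bullet that names 8.1.1 and 8.1.2 collects further reasons to stop. Section 8.1.4 is mainly a permission to continue, so its absence from that bullet says little.
3. The amendment marked text not applicable within 8.1.3, immediately before 8.1.4, and left 8.1.4 unmarked.
4. The change summary describes the 8.1 edit only as making the diagnosis local. That changes who makes the diagnosis. The override clause acts on the changes the amendment made, and no withdrawal of 8.1.4 is among them.

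**TaLG.**

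1. In 5.1.3 the label is applied separately to survival follow-up and to efficacy follow-up, each with its own bullets. The last sentence is not a bullet and concerns treatment.
2. The change summary says 5.1.3 was altered only for survival and efficacy follow-up after the second follow-up visit.
3. The same sentence carries the Week 13 exception, which is live in 8.1.4. Treating the sentence as withdrawn would withdraw a pointer to a live rule.
4. The better reading is therefore that the sentence is live, and it stands to 8.1 as an exception stands to a rule.
5. The difference in vocabulary is one of naming. Under both wordings, a TaLG-only finding was not a recurrence that ended treatment or assessments.

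**Upper bound on size.** Inputs are 26 four-week cycles (Table 2-2), the BCG calendar (Table 7.1.2-1), 27 BCG doses in all (Section 5.4.5), and assessment at Week 14 Day 1 and Week 27 Day 1 (Table 9.1.4-1, itself now not applicable and used here as an assumption).

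- Infusions fall at Weeks 1, 5, 9, ..., 101. Between Week 14 and Week 27 they fall at Weeks 17, 21 and 25, which is 3.
- BCG doses in that span fall at Weeks 14, 15 and 16, which is 3.
- For a TaLG-only finding at the first assessment, the remaining treatment is 26 − 4 = 22 infusions and 7 × 3 = 21 BCG doses, with 159 − 14 = 145 weeks to the week of the last BCG dose.
- Participants: 0.05 × 700 = 35, so fewer than 35 randomized; or 0.05 × 875 = 43.75, so fewer than 44 if the target means enrolled. Anyone in screening at closure is additional.

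The treatment counts are ceilings per participant. They assume a finding at the first assessment and otherwise full completion, and they are not expected effects.

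**Effect on the analysis.** Section 10.3.1 reduces efficacy to listings of investigator assessments. Section 10.3.2 describes safety in treated participants up to 100 days after the last dose actually given. Neither depends on which section the site relied on when it stopped or continued, and no hypothesis is tested.

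**The case for a change.** The best case for a change is that 8.1 is operative text for people still on treatment, that it uses the strongest wording available, and that the amendment touched it while claiming precedence. Elsewhere, in 8.1.3 and 9.1.2.4, the not-applicable label covers several paragraphs to the end of the section. That supports reading the TaLG sentence in 5.1.3 as withdrawn. If it is withdrawn, no live text addresses TaLG by name. The remedy would be text only.

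Part of this stands. The cross-reference is missing. The end of the label in 5.1.3 is not marked, so the live reading of the TaLG sentence is the better one but not the only one. Section 5.1.3 also says Ta where 8.1.4 says TaHG.

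The step from there to harm does not stand. On the Week 13 limb, a site would have to ignore an unmarked subsection that both dosing sections cite. On the TaLG limb, a site would have to record a low-grade finding as recurrence, which is an assumption about local practice, and also set aside 5.1.3. Even if the 5.1.3 sentence is taken as withdrawn, classification passes to the investigator under local standards of care, which is how the amendment handles recurrence generally.

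**Conclusion.** No change to the plan follows. The defect is clerical: one absent cross-reference, one label whose end is unmarked, and one Ta/TaHG mismatch. If the text is reissued for another reason, Sections 5.1.3, 8.1 and 8.1.4 should be reconciled on these points; the clinical rule itself belongs to the clinical team and is not judged here.

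The conclusion rests on three things. First, 8.1.4 is live, which its lack of any label and the two dosing sections support. Second, the last sentence of 5.1.3 is most naturally live, which the change summary supports but does not prove. Third, the study is closed to enrollment and analysed descriptively, so no estimate, test or conclusion depends on the point. Fewer than 35 of the 700 planned had been randomized (fewer than 44 if the target is the 875 enrolled), plus any then in screening. How many had yet to reach Week 13 is not stated and could be zero.

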8.1.1 Nivolumab/Nivolumab-placebo Dose Discontinuation

Nivolumab/nivolumab-placebo treatment must be permanently discontinued per criteria in [Table 7.4-1](#) in [Section 7.4](#). Discontinue nivolumab for any AE, laboratory abnormality, or intercurrent illness which, in the judgment of the investigator, presents a substantial clinical risk to the participant with continued nivolumab dosing.

- Any event that leads to delay in dosing lasting > 10 weeks from the previous dose requires discontinuation, with the following exceptions:
 - Dosing delays to allow for prolonged steroid tapers to manage drug-related adverse events are allowed.
 - Dosing delays lasting > 6 weeks from the previous dose that occur for non-drug-related reasons may be allowed if approved by the BMS Medical Monitor (or designee).

Prior to re-initiating treatment in a participant with a dosing delay lasting > 10 weeks, the BMS Medical Monitor (or designee) must be consulted. Tumor assessments should continue as per protocol even if dosing is delayed. Periodic study visits to assess safety and laboratory studies should also continue every 6 weeks or more frequently if clinically indicated during such dosing delays.

Any adverse event, laboratory abnormality, or intercurrent illness which, in the judgment of the Investigator, presents a substantial clinical risk to the participant with continued nivolumab dosing.

8.1.2 Discontinuation of BCG

BCG treatment should be permanently discontinued for the following:

- Any event requiring discontinuation of nivolumab/nivolumab-placebo as in [Section 8.1.1](#)
- Any AE, laboratory abnormality, or intercurrent illness which, in the judgment of the investigator, presents a substantial clinical risk to the participant with continued BCG dosing
- Systemic BCG reaction (see current BCG prescribing information for description)
- BCG infection (see current BCG prescribing information for description)

Participant may continue nivolumab/nivolumab-placebo treatment if BCG is discontinued.

The duration of treatment with BCG is based on global standard evidence-based guidelines ([Section 5.4.5](#)). Every effort should be made to treat participants with the full course of BCG as defined in the protocol, although if the participant and investigator agree that it is in the participant's best interests to discontinue BCG treatment, the participant should be counselled appropriately and the reason for discontinuation should be documented in the CRF.

8.1.3 Post Study Treatment Study Follow-up

Per Protocol Amendment 01, efficacy follow-up is not required. Participants on efficacy follow-up at the time of Protocol Amendment 01 implementation at each site will conclude efficacy follow-up. Local standard of care assessments should be followed.

Participants will be followed for assessment of safety through 100 days post last dose of study treatment.

Not applicable per Protocol Amendment 01:

In this study, EFS is a key endpoint of the study. Post study follow-up is of critical importance and is essential to preserving participant safety and the integrity of the study. Participants who discontinue study treatment must continue to be followed (in this study or a rollover study) for collection of outcome and/or survival follow-up data as required and in line with [Section 5](#) until death or the conclusion of the study.

BMS may request that survival data be collected on all treated/randomized participants outside of the protocol-defined window ([Section 2, Table 2-3](#)). At the time of this request, each participant will be contacted to determine his/her survival status unless the participant has withdrawn consent for all contacts or is lost to follow-up.

